### **5.1.7. Week 26**

Week 26 in this document refers to the completion of the treatment period, which might not be exactly the 26th week, e.g. if due to treatment delay/use of + 3 days of out of window visit allowance more than 2 times. Efficacy assessments before the safety follow up will all be included in “at week 26”, or “by week 26” analyses unless otherwise specified.

## **5.2. Methods for Handling Missing Data**

Refer to Section 9 for detailed date imputation guidelines.

## **5.3. Windowing of Visits**

Data will be summarized by visit week defined in the protocol when appropriate (e.g. lab parameters).

## **5.4. Protocol Deviations**

All protocol deviations will be entered into eTMS by site staff. The study team will have a blinded review of protocol deviations to determine their classification (important, not important) periodically. Prior to the database lock, the study team will assess impact of all important protocol deviations on the efficacy or ethical conduct and whether they should be excluded from the per-protocol analysis set.

The number of important protocol deviations and the number of subjects with at least one important protocol deviation will be summarized by treatment group. Also, the number of subjects with at least one important protocol deviation with/without a potential impact on efficacy will be summarized by treatment group. The protocol deviation criteria types will also be summarized, with reference to the evaluability document.

All protocol deviations will be presented in by-subject listings, and subjects with protocol deviations that lead to exclusion from the per-protocol analysis set will be flagged.

## **6. STATISTICAL METHODOLOGY**

### **6.1. Study Populations**

A summary of analysis sets by treatment and overall will be presented along with percentages relative to all randomized subjects.

- Subjects randomized
- Subjects in the safety analysis set
- Subjects in the mITT analysis set
- Subjects in the PP analysis set

### **6.2. Subject Disposition**

The number and percentage of subjects will be tabulated for the treatment discontinuation status for the safety analysis set by treatment and overall:

- Subjects who completed study treatment
- Subjects who discontinued early from study treatment

Reasons for early treatment discontinuation will be summarized by the following categories collected on the electronic case report form (eCRF):

- adverse event (AE)
- death
- lack of efficacy
- lost to follow-up
- non-compliance with study drug
- physician decision
- pregnancy
- protocol deviations
- sponsor decision to terminate study
- withdrawal by subject and
- other

The number and percentage of subjects will be tabulated for the end of study status for the safety analysis set by treatment and overall:

- Subjects who completed study
- Subjects who are still on study
- Subjects who terminated study early

Reasons for early study termination will be summarized by the following categories collected on the eCRF:

- adverse event
- death

- lack of efficacy
- lost to follow-up
- non-compliance with study drug
- physician decision
- pregnancy
- protocol deviation
- study terminated by sponsor
- withdrawal by subject
- other

In addition, time from randomization to last study assessment (weeks) will be summarized descriptively.

By-subject listings will be provided for study disposition including days on study, eligibility, and discontinuation from treatment and study reasons.

### **6.3. Demographics and Baseline Disease Characteristics and History**

Demographic and other baseline characteristics will be summarized by descriptive statistics for each treatment group and overall for the SAF. They will also be presented in by-subject listings.

Descriptive statistics will be provided for the following:

- age
- weight (kg)
- height (cm)
- body mass index (BMI) (kg/m^2)

Frequency tabulations will be presented as collected in the eCRF for:

- age (< 65 years or ≥ 65 years)
- sex
- race
- ethnicity
- substance use (tobacco) history (cigarettes, cigars, pipes, or chewing tobacco).

Disease history such as disease status (new-onset or relapsing/refractory), prior GCA (yes/no), biopsy (yes/no), imaging (yes/no), and prior treatment will be summarized using frequencies and percentages and presented in by-subject listings. Time since diagnosis to randomization (month), ESR value for eligibility and at baseline, and CRP value for eligibility and at baseline (local and central separately) will be summarized by descriptive statistics.

### **6.4. Medical History**

Medical history data will be coded according to the Medical Dictionary for Regulatory Activities (MedDRA) version 21.0 before database lock. Medical history data will be summarized for the SAF

by treatment group and overall, by system organ class (SOC) and preferred term (PT) in descending frequency for overall. Subjects with multiple occurrences of the same medical condition will be counted once per each unique SOC and unique PT.

All medical history data will be listed by subject.

## 6.5. Prior and Concomitant Medications

Prior medication is defined as medication with at least one dose taken before the date of the first dose of study drug.

Concomitant medication is defined as medication with at least one dose taken between the date of first dose (inclusive) and the date of last dose date of study drug + 90 days (inclusive) of study drug.

Post-treatment medication will be defined as medications taken after the last dose of study drug.

Additionally, the medications will be considered concomitant if the start date of the medication is missing.

A medication that started prior to the first dose of the study drug and continued after last dose date will be considered as prior, concomitant, and post treatment.

Prior and concomitant medications will be coded using WHO Drug Dictionary WHODrug version Enhanced 01Mar2018 B3 and will be classified by Anatomical Therapeutic Class (ATC) level 2 and preferred term (PT) for the Safety Analysis Set. Frequencies and percentages of subjects using each concomitant medication will be presented by treatment group. Subjects taking the same medication multiple times will be counted once per medication. All medication use will be listed regardless of the timing of the start of the medication.

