8.7 Eligibility Criteria

8.7.1 Inclusion Criteria

To be eligible to participate in the trial, a subject must meet all of the following criteria:

Inclusion Criteria

1. Able and willing to provide written informed consent and to comply with the study protocol
2. Age of ≥ 50 to 85 inclusive

3. Diagnosis of new-onset or relapsing GCA classified according to the following criteria:

New-onset: Initial diagnosis of GCA within 6 weeks of Day 0

- a) Westergren ESR > 30 mm/hour or CRP \geq 1 mg/dL
- b) AND at least one of the following:
 - i. Unequivocal cranial symptoms of GCA (new-onset localized headache, scalp or temporal artery pain or tenderness, ischemia-related vision loss, or otherwise unexplained mouth or jaw pain upon mastication)
 - ii. Unequivocal extracranial symptoms of GCA such as claudication of the extremities
 - iii. Symptoms of PMR, defined as shoulder and/or hip girdle pain associated with inflammatory morning stiffness
- c) AND at least one of the following:
 - i. TAB or ultrasound revealing features of GCA
 - ii. Evidence of large-vessel vasculitis by angiography or cross-sectional imaging study such as MRI, CT/CTA, or PET-CT of the aorta or other great vessels

Relapsing: Diagnosis of GCA > 6 weeks before Day 0 AND

Active GCA within 6 weeks of Day 0 defined as clinical sign/symptom(s) and Westergren ESR > 30 mm/hour or CRP \geq 1 mg/ dL

Refractory nonremitting: Diagnosis of GCA > 6 weeks before Day 0 AND

No remission since the diagnosis of disease as per clinical expectations i.e. Presence of sign/symptoms as per above and Westergren ESR > 30mm/hour or CRP \geq 1 mg/dL within 6 weeks of Day 0

4. Remission of GCA at or before Day 0 (resolution of GCA symptom(s) and CRP < 1.0 mg/dL or ESR < 20 mm in the first hour), such that the subject can safely participate in the study and follow the protocol defined procedures, including initiation of the prednisone taper at the protocol-specified starting dose (i.e., \leq 60 mg/day)
 5. At Day 0, receiving or able to receive oral prednisone up to 60 mg/day for the treatment of active GCA
 6. If using MTX, oral or parenteral up to 25mg/week is permitted during screening if started more than 6 weeks prior to Day 0 and should be tapered to zero by Day 0.
 7. Willing to receive antiplatelet therapy depending on the Investigator's decision
 8. Willing to receive treatment for prevention of corticosteroid-induced osteopenia/osteoporosis depending on the Investigator's decision

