### **2.3. Per Protocol (PP) Analysis Set**

All mITT subjects without important protocol deviations deemed to impact efficacy or ethical conduct will be included in the PP analysis set and will be determined before unblinding. Subjects who had steroid therapy increase for at least 5 mg/day for at least 1 week or took prohibited GCA medication during the treatment period before a protocol-defined flare or end of treatment, whichever occurred first, will be excluded from the PP analysis set.

In this study, subjects are at prednisone doses between 20 mg/day and 60 mg/day at time of randomization. For this dose range and under a tapering schedule of 6 months, which is shorter than what is considered standard of care (1 year or longer), a prednisone dose increase of 5mg or greater is considered a clinically significant change for the purposes of this SAP. Typical GCA corticosteroid taper protocols can be found in ([Docken, 2020](#)).

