##### **Incomplete Start Date:**

*Missing day, month, and year*

No imputation will be made; the corresponding AE will be included.

*Missing day and month*

- If the year is the same as the year of the first dose date, then impute day and month as the day and month of the first dose
- If the year is prior to the year of the first dose date, then impute day and month as 31 Dec
- If the year is after the year of the first dose date, then impute day and month as 01 Jan.

*Missing day only*

- If the month and year are the same as those of the first dose date, then impute day as the day of the first dose date
- If either the year of partial date is before the year of the first dose date, or the years are the same, but the month of partial date is before the month of the first dose date then impute day as last day of the month
- If either the year of partial date is after the year of the first dose date, or the years are the same, but the month of partial date is after the month of the first dose date, then impute day as first day of the month.

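### SAP 6.5 classes every medication with a missing start date as concomitant, even when a recorded stop date places it wholly before first dose

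*SAP*

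**What the plan says.** SAP 6.5 sets out three overlapping medication classes. On prior use it says: "Prior medication is defined as medication with at least one dose taken before the date of the first dose of study drug". Concomitant use is "medication with at least one dose taken between the date of first dose (inclusive) and the date of last dose date of study drug", extended by 90 days. Post-treatment use is anything taken after the last dose. One drug may fall into more than one class.

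A default for missing dates follows: "Additionally, the medications will be considered concomitant if the start date of the medication is missing". It does not mention the stop date.

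The classification feeds a summary on the Safety Analysis Set: "Frequencies and percentages of subjects using each concomitant medication will be presented by treatment group". The same section also lists all medication use, whenever it started.

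For adverse events, SAP 9.1.1 deals with a start date lacking day, month and year in this way: "No imputation will be made; the corresponding AE will be included". Again there is no stop-date condition. For partly missing dates, the general rules in SAP 9.1 do use the stop date: an imputed start that falls after a known stop is moved back to the stop.

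**The concern.** Counting a medication as concomitant when its timing is unknown is the usual cautious default. Here the timing is not always unknown. If the stop date is recorded and falls before first dose, the record itself shows that there was no on-study use. The default discards that information and overrides the definition stated just before it.

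This trial is likely to contain stopped earlier treatments. The aim is for half the subjects to have relapsing disease. Earlier biologics are permitted after a washout (Protocol 8.7.2), and methotrexate is permitted in screening but "should be tapered to zero by Day 0" (Protocol 8.7.1). What is at stake is the accuracy of a by-arm safety table in which a drug stopped before the study can appear as use during it.

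**Working it through.** The plan gives no figure for this point, so there is none to reproduce. The check applies the rules as written to constructed records. I read *missing* in 6.5 as wholly missing.

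**Inputs**
- Concomitant window: first dose to last dose + 90 days (SAP 6.5).
- Missing-start default: concomitant (SAP 6.5).
- Illustrative dates, not from the documents: first dose 1 March 2020, last dose 30 August 2020.

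**Medication records**

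| Record | Start | Stop | Meets the 6.5 definition? | 6.5 as written | With a stop-date exception |
|---|---|---|---|---|---|
| a | missing | 15 Jan 2020 | no | prior and concomitant | prior only |
| b | missing | 1 Apr 2020 | yes | concomitant | concomitant |
| c | missing | missing | cannot be known | concomitant | concomitant |
| d | 1 Dec 2019 | 15 Jan 2020 | no | prior only | prior only |

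Records a and d stop on the same day and differ only in whether the start date was captured, yet 6.5 classifies them differently. Only record a changes under the exception. Records b and c keep the cautious classification.

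**Size per record**
- Planned arm sizes: 42 KPL-301 and 28 placebo (Protocol 8.6).
- One misclassified subject adds 1/42 = 2.4% to a row in the KPL-301 column, or 1/28 = 3.6% in the placebo column.
- The number of such subjects cannot be derived from the documents.

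**Adverse events, side by side**
- Partial start: only the year (2020) is known and the stop is before 1 March 2020. SAP 9.1.1 imputes the start as the first dose date, SAP 9.1 resets it to the stop date, and the event is not treatment-emergent. The rule works.
- Wholly missing start with a stop before first dose: SAP 9.1.1 says the event is included. It neither begins nor worsens after first dose, as SAP 6.8.1 requires for treatment emergence. Protocol 13.4 says events between consent and Day 0 are censored in analysis, and SAP 7.1 lists no departure from that. The texts point to exclusion from the treatment-emergent tables, but 9.1.1 does not say so.

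**The case against.** The strongest reply is that the reach is very small. The flag drives a descriptive table. The drug still counts as prior, the listings show the recorded dates, and prior treatment is summarised separately (SAP 6.3). There is no evidence that any record has a missing start and a known pre-dose stop. All of this stands, and it is why the point is minor. It does not remove the conflict between two sentences of the same section.

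Three stronger readings are tempting, and the documents do not support them.

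- **Subjects wrongly lost from the per-protocol set.** SAP 2.3 excludes a subject who "took prohibited GCA medication during the treatment period before a protocol-defined flare or end of treatment". That criterion has its own window and does not refer to the 6.5 flag. Membership is settled before unblinding, and deviations are reviewed blinded (SAP 5.4). A drug with a recorded stop before first dose was not taken in the treatment period.
- **Apparent use of prohibited medication.** Protocol 10.2 bars introducing the listed drugs from screening onward. A drug begun earlier and stopped before first dose is not an introduction. Methotrexate is also a poor example, because inclusion criterion 6 requires its start to be placed more than 6 weeks before Day 0.
- **Screening events counted as treatment-emergent.** SAP 9.1.1 says only that the event is included. SAP 6.8.1 and Protocol 13.4 both point the other way.

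One caveat remains. SAP 5.2 sends the reader to Section 9 for date rules, and the text available to me ends with adverse event stop dates. A separate medication-date rule after that point cannot be excluded. Section 6.5 itself carries no exception and no cross-reference to one.

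**Conclusion.** The point holds in a narrow form. Applied as written, SAP 6.5 gives a wrong classification for one type of record: start date missing, stop date known and before first dose. This is a stated rule that conflicts with the section's own definition, and more than an omitted detail.

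The consequence is limited to the by-arm concomitant medication table, at 2.4 or 3.6 percentage points of a row per affected subject under the planned allocation. Because the number of affected records is unknown, no total effect should be quoted. The cumulative steroid dose has its own starting point at first dose (SAP 6.7.3.5), and the primary analysis does not use the flag. The adverse event wording is a secondary matter of alignment, since the governing definitions already point to the right result.

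The conclusion assumes that *missing* in 6.5 means wholly missing and that no medication-date rule elsewhere in Section 9 overrides it.

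**What to change.** In SAP 6.5, replace the missing-start sentence with: *A medication with a missing start date is concomitant unless its stop date is before the first dose date, in which case it is prior only.*

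As a secondary alignment in SAP 9.1.1: *An AE with a wholly missing start date is included as treatment-emergent unless its stop date is before the first dose date.* This makes 9.1.1 consistent with SAP 6.8.1 and Protocol 13.4.

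The cost is two clauses and one added condition in each derivation program, ideally made before database lock. Records with a missing or later stop date keep their cautious classification, so nothing is lost.

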## 6.6. Study Treatments and Extent of Exposure

Study drug exposure, prednisone taper exposure, and escape therapy will be summarized descriptively for the SAF by treatment and for overall. Cumulative steroid dose combining information from both prednisone taper and escape therapy will be summarized as efficacy endpoints and be further discussed in Section 6.7.3.5.

### 6.6.1. Treatment Duration

Duration of treatment (weeks) = (last dose date of drug – first dose date of drug + 1) / 7.

It will be calculated for study drug and corticosteroid taper respectively.

### 6.6.2. Cumulative Dose

Cumulative dose (mg) is defined as sum of all doses taken. The dosage will be counted as 0 for days when the drug is not taken/injected. It will be calculated for study drug, prednisone taper, and steroid respectively. Cumulative study drug and prednisone taper will be calculated during treatment period. Cumulative steroid doses will be calculated at the end of week 26 and at the end of the safety follow up.

For the study drug, one partial injection is considered half of the full dosage.

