Subjects who experience a flare or subjects who cannot adhere to the protocol-defined steroid taper due to a flare should be managed to ensure the best possible care of the subject:

- The subject must discontinue the assigned study drug (KPL-301 or placebo) and should receive escape therapy in accordance with local SoC, as determined by the Investigator, which may include, for example, dose modifications of corticosteroids, other immunomodulatory agents, and/or approved therapies (e.g., tocilizumab). The dosages of all concomitant medications used to treat the GCA flare must be entered into the eCRF.
- Escape corticosteroid therapy can be escalated immediately. Due to possible safety and pharmacologic effects resulting from overlapping exposures to immunomodulatory agents on top of co-administered corticosteroids, the investigator should consider a washout period of at least 35

days (based on elimination half-lives) after the last dose of study drug if deemed clinically appropriate.

Any subject who prematurely discontinues the study drug treatment for safety or other reason will have an End-of-Treatment (EOT) visit and will be followed for the intended duration of study treatment (i.e., through Week 26 and Washout Safety Follow-up) to address potential issues of informative censoring. Any subject who withdraws consent from the trial (i.e., all study procedures in addition to study drug administration) must complete at a minimum the Final Washout Safety Follow-up visit 84 ± 3 days from the last dose administered. Additional follow up using public records may be captured where possible.

Washout Safety Follow-up:

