### 1.2. Study Design

This Phase 2 randomized, placebo-controlled Proof of Concept (POC) study will evaluate the efficacy and safety of KPL-301 coadministered with a 26-week corticosteroid taper in subjects with GCA. The study will consist of an up to 6-week screening period, a 26-week double-blind placebo-controlled period during which subjects will receive blinded KPL-301 or placebo coadministered

with corticosteroid taper, and a 12-week washout safety follow-up period during which subjects will discontinue and wash off blinded KPL-301 or placebo.

Approximately 70 subjects with GCA will be randomized to receive KPL-301 or placebo at a 3:2 allocation ratio stratified by disease status (new-onset or relapsing/refractory). Subjects randomized to KPL-301 will receive the drug 150mg every other week by subcutaneous (SC) injection co-administered with a 26-week steroid taper.

Subject who cannot adhere to the protocol-defined steroid taper due to flare/relapse must discontinue study drug (KPL-301 or placebo) and should receive escape therapy in accordance with local SoC per the Investigator. Escape therapy may include, for example, prednisone or similar > 60mg/day, IV corticosteroids, other immunomodulatory agents, and/or approved therapies (e.g., tocilizumab).

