#### **6.7.3.5. *Cumulative steroid dose at Week 26 and at the End of the Washout Safety Follow-up Period***

The cumulative corticosteroid dose from first dose date of study drug to Week 26 will be compared between the treatment descriptively, and analytically using analysis of covariance (ANCOVA). The stratification factor and the corticosteroid starting dose will be the covariates in the model for treatment comparisons. The analyses will include 95% CIs for the difference of the mean cumulative steroid doses between the treatment groups.

Similar analysis will be conducted for cumulative steroid dose from first dose date to the end of the washout safety follow up period.

The average daily dose during the same periods will be summarized descriptively.

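### Cumulative steroid dose adds milligrams of different corticosteroids without conversion, and its Week 26 confidence interval is modestly too narrow if flare rates differ as planned

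*SAP*

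**What the plan says.** SAP 6.6.2 gives one definition for study drug, prednisone taper and steroid alike: "Cumulative dose (mg) is defined as sum of all doses taken". SAP 6.6 states what enters the steroid total: "Cumulative steroid dose combining information from both prednisone taper and escape therapy will be summarized as efficacy endpoints". SAP 1.2 and protocol 10.3 leave the choice of escape agent open: "Escape therapy may include, for example, prednisone or similar > 60mg/day, IV corticosteroids". On data capture, the protocol synopsis (Base Treatment Period) says: "The dosages of all concomitant medications used to treat the GCA flare must be entered into the eCRF". No conversion is mentioned at any of these places. The one reference to prednisone equivalents in the current protocol text (synopsis, Test Products) concerns steroids taken before inclusion.

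For the analysis, SAP 6.7.3.5 specifies an ANCOVA of cumulative dose to Week 26: "The stratification factor and the corticosteroid starting dose will be the covariates in the model for treatment comparisons". It asks for a 95% CI for the difference in means, and for a similar analysis to the end of washout. It names no unequal-variance, robust, transformed or rank-based method. SAP 5 sets confidence intervals to the SAS default unless stated otherwise; for an ANCOVA that is a single pooled residual variance. In the testing order of SAP 3.2, the Week 26 dose is fifth among the secondary endpoints and the washout dose is ninth and last.

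**The concern.** The effect on cumulative corticosteroid dose is the first secondary objective listed in both documents, and the mean difference with its CI will be the reported measure of steroid sparing.

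**Unit.** Followed literally, the definition counts 1 mg of any corticosteroid as 1 mg of prednisone. A flare requires stopping study drug and leads to escape therapy, so escape users should be more numerous on placebo, and the unit error need not cancel between arms. The average daily dose (SAP 6.6.3) inherits it. If a programmer converts anyway, the factors would be chosen outside the SAP, possibly after unblinding.

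**Variance.** Extra steroid comes mainly from flares. The arm with more planned flares is also the smaller arm. A pooled variance understates the standard error in that configuration.

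**Working it through.** **Inputs from the documents.** Flare-free at Week 26: 50% placebo, 85% KPL-301 (SAP 1.3). Planned arms: 28 and 42 (protocol 8.6). Taper schedule: protocol Table 3. The documents give no mean, SD or power for cumulative dose.

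**Planning figures.** HR = ln(0.85)/ln(0.50) = 0.2345. With 20 events, 3:2 allocation and two-sided 0.05, Schoenfeld's formula gives power Φ(√(20 × 0.6 × 0.4) × 1.450 − 1.96) = 88.8%; Freedman's gives 87.3%. Both agree with the stated 87%. Expected flares are 28 × 0.50 = 14 on placebo and 42 × 0.15 = 6.3 on KPL-301, 20.3 in all.

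**Scale.** Summing Table 3 over 7-day weeks gives scheduled totals of 1,312.5 mg (20 mg start) to 2,712.5 mg (60 mg start).

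**Unit error in the mean difference.** If both arms use the same agents and amounts per flare:

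error = (0.50 − 0.15) × share of flares given a non-prednisone steroid × mg given × (factor − 1)

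Share, amount and factor are assumptions; 1.25 is an assumed factor for methylprednisolone.

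| Share | mg given | Factor | Error |
|---|---|---|---|
| any | any | 1 (prednisone only) | 0 |
| 15% | 1,500 | 1.25 | 0.35 × 0.15 × 375 ≈ 20 mg |
| 30% | 1,500 | 1.25 | 0.35 × 0.30 × 375 ≈ 39 mg |
| 25% | 3,000 | 1.25 | 0.35 × 0.25 × 750 ≈ 66 mg |

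In a simulation of the last row the difference was −607 mg raw and −673 mg converted, so the raw sum shrinks the apparent KPL-301 benefit. A factor below 1 reverses the sign.

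**Pooled variance, closed form.** If each flare adds a fixed amount, the flare-driven variance is proportional to p(1 − p): 0.25 on placebo and 0.15 × 0.85 = 0.1275 on KPL-301, a ratio of 1.96.

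- Pooled variance: (41 × 0.1275 + 27 × 0.25)/68 = 0.1761
- Pooled SE²: 0.1761 × (1/42 + 1/28) = 0.01048
- True SE²: 0.1275/42 + 0.25/28 = 0.01196
- SE ratio: √(0.01048/0.01196) = 0.936
- Coverage: 2Φ(1.96 × 0.936) − 1 = 93.3%

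For other variance ratios:

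| Ratio | SE ratio | Coverage |
|---|---|---|
| 1 | 1.00 | 95.0% |
| 1.5 | 0.96 | 94.0% |
| 3 | 0.90 | 92.3% |
| 4 | 0.88 | 91.7% |

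**Simulation from Table 3.** 4,000 trials per case, exponential flare times, uniform starting doses and assumed escape patterns; ANCOVA on stratum and starting dose:

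| Escape pattern (15% vs 50% flares) | Residual variance ratio | Pooled coverage | HC3 coverage |
|---|---|---|---|
| All re-enter taper at 60 mg | 2.03 | 93.2% | 95.0% |
| Mixed oral re-entry | 2.28 | 93.0% | 95.2% |
| Mixed oral, plus IV pulse in 25% of flares | 2.54 | 91.2% | 93.3% |

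With 50% flares in both arms, pooled coverage was 94.8 to 95.3% and the rejection rate 4.7 to 5.3%.

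A second set (3,000 trials per case, gamma-distributed escape doses with mean 1,500 mg, and 0, 15 or 30% IV pulses) gave pooled coverage of 93.6, 92.7 and 93.0%, against 96.0, 95.1 and 95.3% with HC3.

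**The case against.** The definition in SAP 6.6.2 is a general exposure rule that is silent on conversion; it does not set out to mix agents. The documents permit non-prednisone escape but do not predict it. A reader might infer that the placebo total is simply mis-measured. The documents do not support that: the error needs a non-prednisone steroid, it can fall on KPL-301 escape users too, and in the worked examples it works against KPL-301. A figure such as 375 mg for one course is a single subject's under-count, not the error in the endpoint.

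On variance, equal variance is inferred from ANCOVA plus the SAS-default rule and is not stated. The 0.25 and 0.1275 are variances of a flare indicator, not of dose. A reader might also infer an inflated false-positive rate. That does not follow: with equal flare rates the test holds its level. HC3 is not perfect either; it over-covers in one simulated case (96.0%) and still under-covers in another (93.3%). The Week 26 dose is tested only if the primary and four earlier secondary endpoints succeed, in a proof-of-concept trial.

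Most of this stands, and it limits the claim to a conditional and modest one. It does not supply the missing unit rule. Nor does it change the direction of the interval error under the trial's own planning assumptions.

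**Conclusion.** The point holds in a limited form. As written, the steroid total has no common unit once a non-prednisone escape steroid is used. The resulting error in the mean difference is about 20 to 66 mg under the assumed methylprednisolone patterns, zero with prednisone alone, and of either sign in general.

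The Week 26 interval is modestly too narrow if flare rates differ as planned: SE about 6% too small and coverage about 93% from flare variance alone, and 91 to 94% across the simulated escape patterns. This concerns the accuracy of the reported interval; it is not evidence of a false-positive problem.

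The variance argument should not be carried over to the washout endpoint. Prednisone is then at the investigator's discretion in both arms (protocol 8.4.2), so no variance ratio can be derived.

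**What to change.** In SAP 6.6.2, define the steroid total in prednisone-equivalent mg. Append one conversion table, fixed before unblinding, and apply it to every systemic corticosteroid record in the total. In SAP 6.7.3.5, keep the ANCOVA estimate and covariates, but compute the CI and p-value with arm-specific variances or heteroscedasticity-robust (for example HC3) standard errors.

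The cost is a table and a changed variance option; no new data are needed. The robust interval is about 10% wider (11 to 13% in the Table 3 simulations: 206/186, 147/132 and 338/300 for the mean SEs). Power for this endpoint falls by about 5 to 6 points in the gamma-dose simulations (for example 79.6% to 74.3%) and by about 4 to 10 points in the Table 3 simulations (84.3% to 80.4% at the least, 60.5% to 50.0% at the most).
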